1. Title

A randomized, open-label, controlled trial to evaluate efficacy and safety of a highly selective semipermeable membrane (AN-69 Oxiris) in comparison with a semi selective semipermeable membrane (standard AN-69) in COVID-19 associated acute kidney injury: oXAKI-COV study.

2. Number and version

V1.04, October 17th, 2020

3. Type of research

Randomized controlled trial

2-group design

Follow-up study

Prospective

Interventional

Multicentric

Open-label

4. Research group

5. Participating institutions

INCMNSZ. Research study workplace and place of treatment administration.

6. Financial support: neither grants nor payment for researches.

7. Abstract

Title: Randomized, open-label, controlled trial to evaluate efficacy and safety of a highly selective semipermeable membrane (AN69-Oxiris) in comparison with a selective semipermeable membrane ( standard AN69) in COVID-19 associated acute kidney injury: oXAKI-COV study

Rationale: Acute kidney injury (AKI) in critically ill mechanically ventilated patients with COVID-19 disease, is present in up to 30% of this group and more than 50% of them will need renal replacement therapy in the form of continuous renal replacement therapy (CRRT). Acute kidney injury in this context seems to be a marker of multiorgan dysfunction and it produces increased mortality in this population. There is a vast amount of mechanisms that lead to AKI in critically ill patients with COVID-19; however, the cytokine storm could be the strongest mechanism implicated in AKI development in individuals with continuous renal replacement therapy requirements. Therefore, blocking or reducing the cytokine storm is thought to be a therapeutic target.

Highly selective semipermeable membranes (AN69-Oxiris) have been shown able to adsorb endotoxins and to eliminate inflammatory cytokines, thus representing a valuable therapeutic option in this infection.

Objective: Change in norepinephrine requirement by at least 0.1 micrograms / kg / min to maintain similar MAP after initiation of CRRT with Oxiris membrane compared to standard AN69 membrane. MAP measurements will be performed hourly and norepinephrine requirement will be recorded at that time.

Study design: Randomized, open-label, controlled trial in critically ill patients with suspected or confirmed COVID-19 disease, AKI, and criteria for continuous renal replacement therapy initiation admitted in any of the two participating institutions. Patients meeting inclusion criteria will be randomized to receive CRRT with AN69-Oxiris membrane or standard AN69 membrane during a 72h period.

## 8. Literature review

On March 11th, 2020 the World Health Organization declared the new coronavirus disease (COVID-19) as a global pandemic. In México, approximately 35% of COVID-19 positive patients require hospital admission and 4.4% do it in the intensive care unit. Acute kidney injury (AKI) in mild to moderate COVID-19 disease seems to be infrequent; in contrast, critically ill patients or those with a severe disease develop AKI in up to 30% of the cases and nearly half of them will need renal replacement therapy in the form of continuous renal replacement therapy (CRRT). AKI in this context seems to be a marker of multiorgan dysfunction and it produces increased mortality in this population.

Multiple mechanisms of AKI in COVID-19 disease have been proposed: direct injury into podocytes and proximal convoluted tubule cells, organ-organ interactions (lung-kidney axis), and cytokine storm. Of them, the severe cytokine-induced injury seems to be the strongest mechanism participating in AKI in this group of severely ill patients with CRRT need thus representing a valuable therapeutic option.

Lately, extracorporeal blood purification therapies have been proposed as a therapeutic tool for cytokine removal in patients with sepsis (prototype of cytokine storm model). Therefore, new membranes with hemoadsorption capacity have been developed and are now commercially available. The first group of membranes used for patients with sepsis and inflammatory systemic response syndrome was high cut-off semipermeable membranes (HCO) followed by non-selective adsorbent membranes, semi selective semipermeable membranes (AN69), and last highly selective semipermeable (especially those with endotoxin and cytokine adsorption, such as AN69-Oxiris). Although these membranes were designed to improve inflammation, they can also be used as a regular filter in CRTT in patients with AKI. These products can be purchased in our country and internationally but there is scant evidence supporting its efficacy to improve clinical outcomes in patients with overt sepsis.

Highly selective semipermeable membranes (AN69-Oxiris) possess a great capacity for endotoxin adsorption and cytokine removal (interleukin 6 [IL-6], tumor necrosis factor- $\alpha$  [TNF- $\alpha$ ], C reactive protein [CRP], and interleukin 1b), representing a valuable therapeutic option in septic shock; these findings have been tested mainly in experimental models. There are human-based studies with non-representative statistical samples in which these membranes appear to improve severity scores without any impact in mortality. This membrane has been used in some regions around the world during the COVID-19 pandemic; recently, Ma et al published two severe COVID-19 patients who were treated with AN69-Oxiris resulting in decreased levels of inflammatory markers (ie, CRP and IL-6) and better lymphocyte counts. However, there is uncertainty in the clinical benefit of those changes.

Given the lack of specific drugs or vaccine targeted for COVID-19 and, taking into account the pathophysiologic basis that supports the use of extracorporeal blood purification therapies to reduce the cytokine storm in COVID-19 infected patients with AKI requiring CRRT, the use of

these membranes could be of clinical utility in the disease. Here our group presents a randomized, open-label, controlled trial to evaluate efficacy and safety of a highly selective semipermeable membrane (AN69-Oxiris) in comparison with a semi selective semipermeable membrane ( standard AN69) in COVID-19 associated acute kidney injury.

## 9. Hypothesis

Research question: In critically ill patients with COVID-19 disease and AKI requiring CRRT, is the AN69-Oxiris membrane of greater benefit to sustain MAP a lower vasopressor dose in comparison with a conventional AN69 standard membrane, after 72 hours of treatment?

Alternative hypothesis: The use of the AN69-Oxiris membrane will decrease vasopressor requirement in at least 0.1 micrograms/kilogram/minute to sustain a stable MAP in contrast with the usage of AN69 standard membrane, in critically ill patients with COVID-19 and AKI requiring CRRT after 72 h of treatment.

## 10. Goals

Primary goal: Change in norepinephrine requirement by at least 0.1 micrograms / kg / min to maintain similar MAP after initiation of CRRT with Oxiris membrane compared to standard AN69 membrane. MAP measurements will be performed hourly and norepinephrine requirement will be recorded at that time.

Exploratory goals:

- Effectiveness of the AN69-Oxiris membrane in reducing interleukin serum levels (IL 6, IL 10, and TNF alpha).

Serum will be taken every 8 hours for its measurement by ELISA method.

- To establish the safety (the same risk infection and bleeding) of using the AN69- Oxiris membrane in patients with AKI and COVID-19 infection who require CRRT.

Gross bleeding events (gastrointestinal or urinary) as well as catheter-associated infection events (criteria according to IDSA) will be recorded.

- Length of stay in UCI among patients who used AN69-Oxiris membrane in compared to the use of a conventional membrane (standard AN-69) in critically ill patients with COVID-19 associated AKI and CRRT requirement.

- To investigate the effect of AN69-Oxiris in reducing 28-day mortality in contrast compared with the effect of a conventional membrane in this population.

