#### 12. Outcomes

Outcomes:

-Primary outcome: to establish the superiority of treatment with the AN69-Oxiris membrane to sustain a similar MAP with a lower requirement of norepinephrine (at least 0.1 micrograms/kg/min) after 72 hours of treatment initiation, in patients with COVID-19 associated AKI requiring CRRT, compared to the usage of a standard AN69 membrane.

-Secondary outcomes:

- To evaluate the effectiveness of the AN69-Oxiris membrane in reducing interleukin serum levels (IL 6, IL 10, and TNF alpha).
- To demonstrate the advantage of the AN69-Oxiris membrane in decreasing 28-day mortality from the start of CRRT.
- To establish the safety of using the AN69-Oxiris membrane in patients with AKI and COVID-19 infection who require CRRT.
- To examine the efficacy of the AN69-Oxiris membrane in reducing the length of ICU stay compared to the use of a conventional membrane (standard AN-69) in critically ill patients with COVID-19 associated AKI and CRRT requirement.

Variables:

Acute kidney injury. Elevation in serum creatinine or decrease in the urinary output according to what is established in the KDIGO guidelines.

Mean arterial pressure. MAP is considered as the perfusion pressure for organs and, a value greater than 60 mmHg is adequate to maintain perfused the organs of an average person. The mean arterial pressure will be registered, either obtained through a peripheral arterial line (calculated from the area under the curve of the arterial pressure graph) or the non-invasive monitor using the oscillometric method.

Furosemide stress test: This term refers to a furosemide bolus of 1 mg/kg (ideal body weight) with subsequent measurement of urine output after 2 hours. It is considered negative when the urine output during this interval is less than 200 ml.

Safety variables:

\* Clotting of the circuit: it is defined as the presence of clots in the circuit lines and/or filter, which condition rise in the transmembrane, pre-filter, or post-filter pressures, warranting a change of the filter.

\* Allergic reaction: the sudden presence of erythema or rash at any time after starting CRRT treatment.

\* Access bleeding: the occurrence of continuous bleeding at the vascular access insertion site any time after the start of CRRT treatment.

\* Catheter-related bloodstream infection: the presence of any microorganism in blood cultures drawn from catheter's lumen.

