### 13. Sample size

The main outcome considered for this study is the mean dose of norepinephrine at 72 hours after CRRT initiation. Previous studies consider that a difference of at least 0.10 micrograms/kg/min without changes in the MAP, in the intervention group compared to the control group, is a meaningful difference to detect.

Standard deviation for norepinephrine: 0.10 micrograms/kg/min.

Type of test: Two-tailed, with a confidence level of 95% and a statistical power of 80%. Solving the following equation to calculate the sample size using the comparison of 2 means method; a total of 34 patients, 17 within each group, is required. If a 10% loss is assumed, the final sample size will be 36 individuals, 18 in the intervention group (AN69 Oxiris membrane), and 18 in the control group (standard AN69 membrane).

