#### 16. Statistical analysis

Descriptive statistics will be used with measures of central tendency and dispersion of the data according to their distribution. The distribution of the variables will be analyzed with the Kolmogorov-Smirnov "Z" test. For categorical variables, frequencies and percentages will be used. For continuous variables with normal distribution, the mean and standard deviation will be shown. In contrast, the median and interquartile range will be used for continuous variables with an abnormal distribution.

The Student's t-test will be used to compare continuous variables between the two groups, in case of a normal distribution. The Mann-Whitney U-test will be performed for groups with an abnormal distribution. The analysis of data inside the same group at different time intervals (baseline vs 72 h) will be carried out using the Student's t-test, Wilcoxon sum of ranks, or McNemar's test, as appropriate.

Multivariate analysis for mortality will be performed using Cox proportional hazards, adjusted for the baseline SOFA score. Statistical analysis and graphs will be obtained using SPSS 19.0 software (Chicago, IL) and Graphpad Prism 5 software (San Diego, Ca), respectively. A p-value <0.05 will be considered significant. An intention-to-treat analysis will be pursued.

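### The plan aims to establish the same risk of infection and bleeding without a margin, interval criterion or between-group method, and 18 per arm can show equal risk only within a wide band; the event definitions also differ between Sections 10 and 12

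*Combined protocol and SAP*

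**What the plan says.** **The aim.** Section 10 lists safety among the exploratory goals, worded "To establish the safety (the same risk infection and bleeding) of using" the Oxiris membrane. Section 12 lists it among the secondary outcomes, worded "To establish the safety of using the AN69-Oxiris membrane in patients with AKI and COVID-19 infection who require CRRT", without the reference to equal risk.

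**The events.** Section 10 states: "Gross bleeding events (gastrointestinal or urinary) as well as catheter-associated infection events (criteria according to IDSA) will be recorded". Section 12 has its own list of safety variables. There, catheter-related bloodstream infection is "the presence of any microorganism in blood cultures drawn from" the catheter lumen, and the only bleeding variable is continuous bleeding at the vascular access site. Circuit clotting and allergic reaction are also defined.

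**The size.** Section 13 states: "The main outcome considered for this study is the mean dose of norepinephrine at 72 hours after CRRT initiation". It requires 17 per arm and, after a loss allowance, "the final sample size will be 36 individuals, 18 in the intervention group" and 18 in the control group.

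**The analysis.** Section 16 summarises categorical variables by frequency and percentage. The t-test "will be used to compare continuous variables between the two groups, in case of a normal distribution", with Mann-Whitney otherwise. McNemar's test appears only in the within-group sentence: "The analysis of data inside the same group at different time intervals (baseline vs 72 h) will be carried out using the" t-test, Wilcoxon or McNemar's test. Cox regression is for mortality. The general threshold is p<0.05.

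**The concern.** Showing that two risks are the same is a different task from failing to show that they differ. It needs a statement of how large a difference would still count as the same, and an interval narrow enough to exclude anything larger. The plan has neither. The rule left to the analyst is p<0.05, with no test named for comparing event proportions between arms. The easy route to the stated conclusion is then a non-significant p-value, which in a trial of this size says little.

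Safety is part of the trial's title, and Section 11 says that the Oxiris filter carries a heparin coating, so bleeding is a natural question to compare by arm. A report that the risks are the same could be made while a large excess remained compatible with the data.

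The definitions add to this. With two descriptions of infection and two of bleeding in an open-label trial, a choice made after events are known by arm would be open to bias.

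**Working it through.** **Inputs.** From Section 13: 18 per arm planned, 17 per arm required before loss; two-sided 5% level, 80% power, difference 0.10 and SD 0.10 micrograms/kg/min for norepinephrine. Infection and bleeding rates: none in the documents, so event counts below are illustrative. Equivalence margin: none in the documents.

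**1. The plan's own figure.** The normal approximation gives n per arm = 2(1.960 + 0.842)² × (0.10/0.10)² = 15.7, so 16. The t-test version gives 16.7, so 17 per arm and 34 in total, as stated. Dividing 34 by 0.9 gives 37.8, so 38 rather than 36; the small gap does not matter here. The size rests on norepinephrine alone, which is normal practice.

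**2. Precision for a safety event.** Wilson limits for x events in n are

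[p + z²/2n ± z√(p(1−p)/n + z²/4n²)] / (1 + z²/n), with p = x/n and z = 1.960.

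Newcombe's interval for the risk difference combines the Wilson limits (l, u) of the two arms. With equal counts it is symmetric, with half-width √[(p−l)² + (u−p)²].

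- 0/18 in each arm: l = 0 and u = 3.8415/(18 + 3.8415) = 0.1759, so the half-width is 17.6 points.
- 2/18 in each arm: p = 0.1111, l = 0.0310, u = 0.3280. The half-width is √(0.0801² + 0.2169²) = 0.2312, or 23.1 points.

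Agresti-Caffo adds one event and one non-event to each arm. With equal counts the half-width is z√[2p̃(1−p̃)/(n+2)], where p̃ = (x+1)/(n+2).

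- 0/18 in each arm: p̃ = 0.05, and 1.960 × √(2 × 0.05 × 0.95/20) = 0.135.

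| Events in each arm | Newcombe, 18 per arm | Agresti-Caffo, 18 per arm | Newcombe, 17 per arm |
|---|---|---|---|
| 0 | ±17.6 | ±13.5 | ±18.4 |
| 1 | ±20.7 | ±18.6 | ±21.6 |
| 2 | ±23.1 | ±22.1 | ±24.1 |
| 4 | ±26.5 | ±26.8 | ±27.5 |

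(95% half-widths in percentage points.)

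**3. All possible results.** There are 19 × 19 = 361 pairs of counts at 18 per arm. The smallest symmetric band around zero that contains the whole 95% interval is ±17.6 points by Newcombe and ±13.5 by Agresti-Caffo. Both occur only when no patient, or every patient, has the event. The next smallest Newcombe band is ±20.7, at one event in each arm (or 17 in each).

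**4. Unequal counts.** For Oxiris minus control, the Newcombe upper limit is +12.6 points at 0 v 1, +8.2 at 0 v 2 and +4.0 at 0 v 3. For 0 v 3: −0.1667 + √(0.1759² + 0.1083²) = +0.040. The lower limit in that case is −39.2, so such a result bounds excess risk but does not show equal risk.

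**5. What non-significance would mean.** The plan names no test, so Fisher's exact test is assumed. Four events on Oxiris against none on control gives p = 0.10, not significant, while the Newcombe interval runs from +0.2 to +45.2 points. If the true risk doubled from an assumed 10% to 20%, p<0.05 would occur in about 6% of trials.

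**6. Definitions side by side.**

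| Event | Section 10 | Section 12 |
|---|---|---|
| Catheter infection | IDSA criteria | Any microorganism in a catheter-lumen blood culture |
| Bleeding | Gross gastrointestinal or urinary | Continuous, at the access site |
| Status of safety | Exploratory | Secondary |

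**The case against.** The reference to equal risk is a parenthesis in one exploratory goal. It is absent from the hypothesis, Section 12 and Section 16, and no formal equivalence or non-inferiority test is declared. Frequencies and percentages by arm are already most of a descriptive safety analysis. This is fair. It limits the point to wording and reporting, but it does not remove the stated aim or supply a criterion for it.

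A reader might infer that no result at 18 per arm could support the claim, whatever the data show. The documents do not support that, because they set no margin. A margin of about 18 points could be met by no events in either arm. If the question were only excess harm, fewer events on Oxiris could give a small upper limit, such as +4.0 points at 0 v 3. A reader might also infer that the choice of interval makes no difference. It does: at 0 v 0 a 15-point margin is missed by Newcombe and met by Agresti-Caffo, and the 90% Newcombe interval, common for equivalence, is ±13.1. Only the low precision is common to all of them.

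On definitions, the documents do not reproduce the IDSA criteria, so how often the two infection rules would disagree cannot be said. The two bleeding descriptions may be meant to complement each other, but the plan does not say so. The exploratory or secondary mismatch is minor: no alpha depends on it, and it also affects interleukins, ICU stay and 28-day mortality.

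**Conclusion.** The point holds in a limited form. The plan states an aim of equal risk and gives no margin, no interval criterion and no between-group method for event proportions by which to judge it. At 18 per arm, equal risk cannot be shown within a two-sided 95% band narrower than about ±18 points by Newcombe, or ±13.5 by Agresti-Caffo, and either is reached only if no patient or every patient has the event. With two events in each arm the band is about ±23 points by Newcombe. These figures assume full follow-up of 18 per arm and illustrative counts; at 17 per arm they are slightly wider.

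Infection and bleeding are each described differently in Sections 10 and 12, so it is unclear which events would enter the comparison. None of this calls for a larger trial or touches the primary norepinephrine comparison. It should be corrected because it governs what the trial may conclude about safety.

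**What to change.** - **Sections 10 and 12:** change the aim from establishing safety to describing it, and delete the Section 10 parenthesis about equal risk.
- **Section 16:** report every safety event named in either section by arm, as counts and percentages, with the risk difference and one pre-named 95% interval suited to small counts, for example Newcombe. State that a non-significant difference will not be read as equal risk.
- **Definitions:** reconcile infection and bleeding between Sections 10 and 12, so that each event has one stated definition, before any data are compared by arm. If gastrointestinal, urinary and access-site bleeding are all intended, say so and report them separately.
- **Labels:** give each non-primary endpoint the same status, exploratory or secondary, in both sections. This covers interleukins, ICU stay and 28-day mortality as well as safety.

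The cost is a wording change and one reporting table, with no extra patients or data collection. The downside for the sponsor is that the safety conclusion becomes less favourable than the one now stated.

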#### 11. Methods/ to describe resources used

- AN69 hemofilter: it is a semi-selective, semipermeable membrane with a moderate to low cytokine adsorption capacity, but does not remove endotoxins. This membrane is made of polyacrylonitrile (AN69) with a polyethyleneimine treatment.
- AN69-Oxiris hemofilter: It is a highly selective, semipermeable membrane with enhanced capacity for endotoxin and cytokine adsorption. The aforementioned properties are possible given the larger adsorption surface added to the AN69 standard membrane and the presence of a heparin coating that decreases its thrombogenicity and increases its adsorption capacity.

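### Sections 10 and 12 name different bleeding sites and neither covers bleeding elsewhere, so any statement about bleeding risk would rest on an incomplete count

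*Combined protocol and SAP*

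**What the plan says.** Section 10 (Goals) states the safety aim as "To establish the safety (the same risk infection and bleeding) of using the AN69- Oxiris membrane". No bleeding site is named in that aim. The line beneath it says what will be collected: "Gross bleeding events (gastrointestinal or urinary", the bracket closing after those two sites, together with catheter-associated infections by IDSA criteria.

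Section 12 (Outcomes) repeats safety as a secondary outcome, "To establish the safety of using the AN69-Oxiris membrane in patients with AKI and COVID-19 infection who require CRRT", and then defines four safety variables: circuit clotting, allergic reaction, access bleeding and catheter-related bloodstream infection. The bleeding variable is "the occurrence of continuous bleeding at the vascular access insertion site any time after the start of CRRT treatment".

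No other section adds to this. Section 19 (Follow-up variables) has no bleeding item. Section 16 (Statistical analysis) names no bleeding endpoint. No general collection of adverse events or serious adverse events is described.

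**The concern.** The goal is about bleeding as a whole, but the variables meant to serve it cover selected sites, and the two sections select different ones. A reader who works from the defined variables in Section 12 has no gastrointestinal or urinary bleeding to report. A reader who works from Section 10 has no access-site bleeding. A reader who combines them still has nowhere to put a bleed at any other site.

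What is at stake is the meaning of the safety result. The hoped-for conclusion is that the risk is the same on both membranes, and leaving events out makes low and similar counts easier to obtain. The trial is also open-label. Where the written definitions are partial and do not agree, staff who know the allocation must decide which bleeds to log.

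**Working it through.** **The plan's own figures.** No figure in the documents depends on the bleeding definition. The sample size comes from the primary outcome in Section 13: difference 0.10, standard deviation 0.10 micrograms/kg/min, two-sided 5%, power 80%. An exact two-sample t-test calculation gives 16.7, so 17 per arm and 34 in total, as stated. The plan then gives 36 (18 per arm) after a 10% loss; 34/0.9 = 37.8 would round to 38. That difference does not affect this point, and 18 per arm is used below as stated.

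**The sections side by side.**

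| Bleeding site | Section 10 | Section 12 safety variables |
|---|---|---|
| Gastrointestinal | yes, if gross | not listed |
| Urinary | yes, if gross | not listed |
| Vascular access | not listed | yes, if continuous |
| Airway, intracranial, retroperitoneal, other | not listed | not listed |

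The lists have no row in common, and their thresholds differ too (gross against continuous). Together they cover three sites.

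**How likely is an unlisted bleed?** The documents give no bleeding rates, so the rate p of patients with a bleed at an unlisted site is an assumption. Among 36 independent patients, the chance of at least one is 1 − (1 − p)^36:

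- p = 2%: 1 − 0.98^36 = 52%
- p = 5%: 1 − 0.95^36 = 84%
- p = 10%: 1 − 0.90^36 = 98%

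**What an undercount does to the comparison.** Let c be the share of bleeding patients who have a bleed at a listed site, and suppose that c is the same in both arms. True rates p0 and p1 are then counted as c·p0 and c·p1. The ratio p1/p0 is unchanged, but the absolute difference shrinks to c·(p1 − p0). With assumed true rates of 10% and 30%, the difference of 20 points becomes 16 points at c = 0.8 and 10 points (5% against 15%) at c = 0.5. Fisher exact power with 18 per arm is about 21% for 10% against 30%, and about 5% for 5% against 15%. Both c and the rates are illustrative.

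**What 18 per arm can show even with a complete count.** For zero bleeds in 18 patients, the one-sided 95% upper limit solves (1 − p)^18 = 0.05, so p = 1 − 0.05^(1/18) = 15.3%. The upper end of a two-sided 95% interval is 1 − 0.025^(1/18) = 18.5%.

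**The case against.** The strongest reply is that the text never says other bleeding does not count. Neither list contains the word only, the bracket in Section 10 could be meant as examples, and the two sections can be read as additive rather than as rivals. Some of this stands. It would go too far to say that the plan classifies a bleed elsewhere as a non-event, or that its lists are expressly closed. What remains is that the bracket carries no wording to mark it as examples, the sections disagree on sites, and nothing else in the documents would collect other bleeds. Reading the bracket as examples would leave the mismatch with Section 12 in place.

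A reader might also infer that the intervention membrane is the one likely to bleed more, because it has "the presence of a heparin coating that decreases its thrombogenicity and increases its adsorption capacity". The documents do not support that. They link the coating to thrombogenicity and adsorption and say nothing about systemic bleeding, and Section 11 gives regional citrate to both arms.

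Nor do the documents show a bias between arms. If the mix of bleeding sites is alike in both, the ratio is preserved, as shown above. One could also divide the 15.3% limit by an assumed capture share of 80% or 50% to obtain 19.2% or 30.7% for any bleeding. The shares have no source in the documents, and the result is a limit for one arm, not a measure of bias in the comparison.

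Finally, safety is labelled exploratory in Section 10 and secondary in Section 12, and no sample size, margin or decision rule depends on bleeding. That limits the weight of the point but does not remove it.

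**Conclusion.** The point holds as one of incomplete and inconsistent outcome definition. The stated aim is bleeding risk without a site limit. The written variables cover three sites, divided between two sections that do not overlap, and bleeding elsewhere has no category. Following the plan as written would give an incomplete count against its own goal.

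The size of the undercount cannot be derived from the documents. The 52% to 98% range above rests on assumed rates of 2% to 10% and on independent patients; it shows only that a missed bleed is plausible in a trial of 36. That the undercount favours one membrane, or that the coating raises bleeding, is not established.

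A better definition will not let this trial establish equal bleeding risk, since 0 of 18 is still compatible with a true rate of up to 15.3%. It would make the reported count complete and its uncertainty honest. The change should be made, but the primary analysis does not depend on it.

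**What to change.** Use one bleeding variable in Sections 10 and 12: any clinically recognised bleeding at any site, whether overt or confirmed by imaging or a procedure done in routine care. The second limb matters because intracranial and retroperitoneal bleeds need not be overt. For each event record the site and whether red cells were transfused.

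In Section 16, add a comparison by arm of patients with at least one bleed, with a confidence interval suited to small counts. Report bleeds with transfusion separately, so that minor oozing is not weighed the same as a major bleed. Keep gastrointestinal, urinary and access-site bleeding, as now defined, as descriptive subcategories. Word the conclusion as an estimate with its interval, not as a demonstration of equal risk.

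The cost is a change of wording in three sections and two data fields (site, transfusion). No treatment, added test, sample size or primary analysis changes. The downside is slightly more events to record, including minor ones, and in an open-label trial the recognition of minor bleeds can depend on knowing the arm. The separate report of transfused bleeds helps there, although the decision to transfuse is unblinded too.
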